4.1.4 Other secondary endpoints (not alpha controlled)

All other secondary endpoints will be analyzed using the FAS population.

- 1) Proportion of participants who achieve an IGA-BP score of 0 or 1 while receiving efgartigimod PH20 SC or placebo and have been off OCS therapy for ≥8 weeks at week 36: same derivation and presentation as for the primary endpoint taking into account ICEs (composite strategy) and rescue therapy (non-responders).
- 2) Proportion of participants who achieve an IGA-BP score of 0 or 1 while receiving efgartigimed PH20 SC or placebo at any time through week 36: similar derivation and presentation as for the primary endpoint taking into account ICEs (composite strategy): a participant with IGA-BP score of 0 or 1 before ICE (if any) is considered a responder. For participants who received rescue therapy, only assessments prior to or on the start date of rescue therapy will be considered.
- 3) Change from baseline to week 36 in the BPDAI activity and total score will be analysed using the same MMRM model with 'treatment policy strategy' as for the analysis on the Itch NRS score. For participants who received rescue therapy, only assessments prior to or on the start date of rescue therapy will be included in the model.

Descriptive statistics on absolute values, changes from baseline and percent changes from baseline in BPDAI activity and total score will be calculated per analysis visit. For participants who received rescue therapy, only assessments prior to or on the start date of rescue therapy will be considered.

4) Time to CDA, calculated as the difference between the first date CDA was achieved and the first IMP administration date.

Time to CDA (days) = date (first CDA) - first IMP date + 1

Participants who already have CDA at the first IMP administration date (day 1) will be excluded from the analysis. Participants without any post-baseline disease assessment are censored at day 1. Participants with post-baseline disease assessment but not achieving CDA during treatment phase are censored at end of treatment phase.

Participants with a main intercurrent event prior to achieving CDA (composite strategy) and participants who received rescue therapy prior to achieving CDA, will be censored at the planned end of the treatment phase. More specifically, these participants will be censored at the maximum of:

- Day 267 (Week 36 + 2 weeks)
- The latest day CDA was achieved by any participant in the treatment phase

The first date CDA was achieved is the start date of the first episode with disease status CDA or a better disease status (CR while receiving OCS therapy of more than 0.10 mg/kg/day, CR while receiving minimal OCS therapy for less than 8 weeks *or* for at least 8 weeks, CR while being off OCS therapy for less than 8 weeks *or* for at least 8 weeks).

[figure not shown]
Time to CDA will be descriptively presented by treatment group for each stratum and overall with median times, quantiles and number and percentage of participants censored and with event. Both treatment groups will be compared using a stratified Gehan-Wilcoxon statistic.

5) Time to CR, calculated as the difference between the first date CR was achieved and the first IMP administration date. Similar calculations and censoring rules are applied as for 'time to CDA'.

The first date CR was achieved is the start date of the first episode with disease status CR while receiving OCS therapy of more than 0.10 mg/kg/day or a better disease status (CR while receiving minimal OCS therapy for less than 8 weeks *or* for at least 8 weeks, CR while being off OCS therapy for less than 8 weeks *or* for at least 8 weeks).

Time to CR will be analysed in a similar way as 'time to CDA'.

6) Time to CR while on minimal OCS therapy for ≥8 weeks, calculated as the difference between the first date CRmin was achieved and the first IMP administration date. Similar calculations and censoring rules are applied as for 'time to CDA'.

The first date CRmin was achieved is:

- the start date of the first episode with disease status CR while receiving minimal OCS therapy for at least 8 weeks or CR while being off OCS therapy for at least 8 weeks
- or else the start date of the first episode within a sequence of episodes with disease statuses CR while receiving minimal OCS therapy for less than 8 weeks or for at least 8 weeks and CR while being off OCS therapy for less than 8 weeks or for at least 8 weeks + 56 days

whichever comes first.

Time to CRmin will be analysed in a similar way as 'time to CDA', except that a stratified log-rank test will be used for comparing both treatment groups (instead of the stratified Gehan-Wilcoxon statistic).

7) Time to CR/PR while off OCS therapy for ≥8 weeks (CR/PRoff), calculated as the difference between the first date CR/PR while off OCS therapy for ≥8 weeks was achieved and the first IMP administration date. Similar calculations and censoring rules are applied as for 'time to CDA'.

The first date CR/PR while off OCS therapy for ≥8 weeks was achieved is:

- the start date of the first episode with disease status CR while being off OCS therapy for at least 8 weeks or PR while being off OCS therapy for at least 8 weeks
- or else the start date of the first episode within a sequence of episodes with alternating disease statuses CR while being off OCS therapy for less than 8 weeks and PR while being off OCS therapy for less than 8 weeks + 56 days

whichever comes first.

[figure not shown]
Time to CR/PR will be analysed in a similar way as 'time to CRmin'.

8) Time to CR while off OCS therapy for ≥8 weeks, calculated as the difference between the first date CR while off OCS therapy for ≥8 weeks was achieved and the first IMP administration date. Similar calculations and censoring rules are applied as for 'time to CDA'.

The first date CR while off OCS therapy for ≥8 weeks was achieved is the start date of the first episode with disease status CR while being off OCS therapy for at least 8 weeks.

Time to CRoff will be analysed in a similar way as 'time to CRmin'.

9) Time from CDA onset to Relapse, calculated only in participants with CDA as the difference between the first date of relapse and the first date CDA was achieved. Similar calculations and censoring rules are applied as for 'time to CDA', except for the handling of intercurrent events and rescue therapies. Main intercurrent events prior to Relapse are ignored (treatment policy strategy) and participants who received rescue therapy prior to Relapse will be censored at the start of the rescue therapy.

Time from CDA onset to Relapse will be analysed in a similar way as 'time to CRmin'.

10) Time from CR onset to Relapse, calculated only in participants with CR as the difference between the first date of relapse and the first date CR was achieved. Similar calculations and censoring rules are applied as for 'time from CDA to Relapse'.

[figure not shown]
Time from CR onset to Relapse will be analysed in a similar way as 'time to CRmin'.

11) Time from CRoff onset to Relapse, calculated only in participants with CRoff as the difference between the first date of relapse and the first date CRoff was achieved. Similar calculations and censoring rules are applied as for 'time from CDA to Relapse'.

Time from CR onset to Relapse will be analysed in a similar way as 'time to CRmin'.

- 12) NCOD as calculated for the different subperiods. NCOD from CDA/CR onset until relapse will only be analysed in participants with CDA/CR respectively. Same analysis will be performed as for the primary estimand of the key secondary parameter with ICEs handled according a 'while on treatment' strategy.
- COD will be calculated for the on IMP treatment period and the subperiods mentioned before. Only descriptive statistics will be presented.
- 13) Changes from baseline at week 36 in the 24-hour worst Itch NRS score will be analysed in the same way as for the 24-hour average itch score in the key secondary analysis.
- 14) Proportion of participants who received rescue therapy before week 36. A 'treatment policy' approach will be applied by ignoring main ICEs. Same CMH model as proposed for the primary endpoint.
- 15) ABQOL (17 items), EQ-5D-5L (5 dimensions) and DLQI (10 items) are assessed by the investigator at baseline, Week 12, Week 26 and at Week 36/ETD/ESD. Frequency tabulations will be provided for the percentages of participants within each outcome of QoL questionnaire items. Additionally cumulative percentages (starting with the best outcome result) will be calculated. A 'treatment policy' approach will be applied by ignoring main ICEs. For participants who received rescue therapy, only assessments prior to or on the start date of rescue therapy will be considered.
- 16) EQ-5D-5L VAS score and DLQI score are assessed by the investigator at baseline, Week 12, Week 26 and at Week 36/ETD/ESD. A total ABQOL score is calculated as the sum of all 17 items score 0 to 3 with higher score indicating worse condition. Missing items are imputed with the average score of the present items if at least half (9) of the items are present. The total score is rounded to the highest integer. A 'treatment policy' approach will be applied by ignoring main ICEs. For participants who received rescue therapy, only assessments prior to or on the start date of rescue therapy will be considered.

Descriptive statistics on absolute values and changes from baseline for EQ-5D-5L VAS score, DLQI score and Total ABQOL score will be calculated per time point.

The same MMRM model as for the itch NRS score will be applied to analyse these changes from baseline but using a standard unstructured covariance matrix (UN) since there are only 3 post-baseline visits during the treatment-phase.

17) C-GTI: Composite Glucocorticoid Toxicity Index comprises the Aggregate Improvement Score (AIS) and the Cumulative Worsening Score (CWS) (health impact of GC) and is derived at baseline, Week 12, Week 26, and Week 36/ETD/ESD. AIS and CWS are calculated for the first 12 weeks, 26 weeks, and 36 weeks period and overall (period till last post-baseline assessment). Details of AIS and CWS derivations are specified in appendix 9.2.

A 'treatment policy' approach will be applied by ignoring ICEs. For participants who received rescue therapy, only assessments prior to or on the start date of rescue therapy will be considered.

Descriptive statistics will be provided for the C-GTI scores AIS and CWS; treatment groups will be compared at each visit using the same ANCOVA model as for the NCOD analysis. C-GTI will be analysed on complete cases: i.e., participants with C-GTI assessment at baseline and at least one post-baseline visit. Participants where first post-baseline GTI improvements/worsening have not been obtained with respect to the baseline moment but with respect to a later moment (i.e., no GTI assessment at baseline visit) are excluded from analyses and are only listed.

Kaplan-Meier curves will be created for all 'time to event' endpoints.

[figure not shown]
Separate listings will be created for all 'time to event' endpoints, for lesion assessments, for BPDAI assessments and scores, for ABQOL, EQ-5D-5L and DLQI data, for calculated C-GTI scores and for complementary GTI specific list (GTI-SL).

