IGA-BP Investigator Global Assessment of Bullous Pemphigoid

IMP Investigational medicinal product

IM intramuscular

IRR Injection-related reaction
ISR Injection site reaction

IV intravenous

IVIg immunoglobulins given intravenously

LRV Lower reference value

MedDRA Medical Dictionary for Regulatory Activities

MMRM Mixed model for repeated measurements

NAb Neutralizing antibody

ARGX-113-2009 Final and Interim Analysis Final 4.0 of 04NOV2024

NCOD Normalized cumulative OCS dose

Pharmacokinetics

NCI National Cancer Institute
NRS Numerical Rating Scale

OCS Oral corticosteroid
OLE Open-label extension
PD Pharmacodynamics

PBO Placebo

PK

PR Partial Remission

PRO participant-reported outcome

PT preferred term QoL Quality of life

QTc corrected QT interval

QTcF Fridericia's corrected QT interval

rHuPH20 recombinant human hyaluronidase PH20

SAE Serious Adverse Event

SAF Safety analysis set

SAP Statistical analysis plan SBP Systolic blood pressure

SC Subcutaneous

SCR all screened participants analysis set

SD Standard deviation

SE Standard error

SGS CR SGS Clinical Research

SOC system organ class

SOP Standard operating procedure

STAT Statistics

TEAE Treatment-emergent adverse event

TCS Topical corticosteroid

TV Target value

WI Work instruction

WHODD World Health Organization Drug Dictionary

SGS	Statistical Analysis Plan	
ARGX-113-2009	Final and Interim Analysis	Final 4.0 of 04NOV2024

DEFINITION OF TERMS

case report form (CRF)	A printed, optical, or electronic document in which protocol required information is recorded for each study participant.
Complete remission (CR)	The absence of new lesions, complete healing of existing lesions, and absence of pruritus.
Complete remission on minimal OCS therapy (CRmin)	Being in CR for \geq 8 weeks and have been on minimal OCS therapy (\leq 0.10 mg/kg/day of prednisone or an equivalent dose of another OCS) for \geq 8 weeks
Complete remission off OCS therapy (CRoff)	Being in CR for ≥ 8 weeks and have been off OCS therapy for ≥ 8 weeks.
Control of disease activity (CDA)	The point at which new lesions cease to form and established lesions begin to heal, and pruritic symptoms start to abate.
Display	Analysis table, figure or listing.
Minimal OCS therapy	An oral prednisone dosage of \leq 0.10 mg/kg/day (or an equivalent dose of another OCS).
Phase	Interval of time in the planned conduct of a study that is associated with a specific purpose: for example, screening, treatment, follow-up.

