- From CDA onset until Relapse or end of on IMP treatment period (whichever comes first) (Only defined on the subset of participants that achieve CDA during the on IMP treatment period)
- From CR onset until Relapse or end of on IMP treatment period (whichever comes first) (Only defined on the subset of participants that achieve CR during the on IMP treatment period)

Details on how to derive the time till CDA, CR, CRmin, CR/PRoff and CRoff are included in section 4.1.4.

Following rules will be applied to allocate OCS administrations to the correct period:

- Only the start and stop date information will be considered
- Records with (partially) missing dates will be imputed as detailed in section 2.3.2.
- If dates of administration records overlap, the reported doses will be added together.
- If an administration is reported as dose per administration with frequency, then the doses should be allocated to the correct dates, taking the start date and the frequency into account. Example:
 - O Dose: 40 mg
 - Frequency: every other day
 - o Start Stop date: 01JAN2022 03JAN2022

[figure not shown]
This will result in:

- o 40 mg be allocated to 01JAN2022
- o 0 mg allocated to 02JAN2022
- o 40 mg allocated to 03JAN2022

The following parameters will be derived for IMP administration:

- Number of administrations: sum of all administrations of study drug.
 Two administrations are expected on day 1 and day 8.
- Number of loading doses: i.e., daily doses of 2000 mg (2 administrations of 1000 mg).

The following parameters will be derived for IMP self-administration by participant and by caregiver:

- Number of participants/caregivers receiving the self-administration training.
 - Number of training visits received by participant/caregiver.
- Number of participants/caregivers who were adequately trained and capable to self-administer efgartigimod.
- Number of training visits before being considered capable to selfadminister.

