A participant is considered as CRmin at week 36 when the reported disease status at week 36 is 'CR while receiving minimal OCS therapy for at least 8 weeks' or 'CR while being off OCS therapy for at least 8 weeks', or else when the reported disease status at week 36 belongs to a sequence of episodes with disease statuses 'CR while receiving minimal OCS therapy for less than 8 weeks *or* for at least 8 weeks' and' CR while being off OCS therapy for less than 8 weeks *or* for at least 8 weeks', having

SGS	Statistical Analysis Plan		
ARGX-113-2009	Final and Interim Analysis	Final 4.0 of 04NOV2024	

started at least 56 days earlier (and for which within these 56 days the disease status provides evidence that the participant remained in CR and the minimal OCS therapy was maintained).

The same approach for handling the main ICEs (composite strategy), for handling rescue therapies and for handling missing data, as suggested for the primary analysis, will be applied.

5) The Itch NRS is measured over time and changes from baseline in the 24-hour average itch score will be analysed. A 'treatment policy' approach will be applied by ignoring the main ICEs. For participants who received rescue therapy, only assessments prior to or on the start date of rescue therapy will be included in the analysis.

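### SAP 4.1.4 items 6 and 7 date an 8-week remission at sequence start + 56 days without requiring the sequence to last 56 days, so a short remission ending in relapse can be recorded as an event

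*SAP*

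**What the plan says.** SAP 4.1.4 item 6 gives two routes to the date on which CRmin was first achieved and takes the earlier.

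- **First route:** the start of an episode whose reported status is already CR for at least 8 weeks, on minimal OCS or off OCS.
- **Second route:** "the start date of the first episode within a sequence of episodes with disease statuses CR while receiving minimal OCS therapy", with a list of statuses that runs through "CR while being off OCS therapy for less than 8 weeks or for at least 8 weeks + 56 days". Statuses of less than 8 weeks are therefore admitted. Nothing is said about how long the sequence must run or how it ends.

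Item 7 (CR/PR off OCS) has the same two-route structure. Its second route again looks for an opening episode, here one lying "within a sequence of episodes with alternating disease statuses CR while being off OCS therapy for less than 8 weeks". The status list in that bullet closes with "PR while being off OCS therapy for less than 8 weeks + 56 days".

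Two other places in the SAP do state a duration.

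- The Definition of terms makes CRmin a state of CR for at least "8 weeks and have been on minimal OCS therapy" for at least 8 weeks.
- For CRmin at week 36, SAP 4.1.3.1 item 4 also uses a sequence of episodes, but one that "started at least 56 days earlier (and for which within these 56 days the disease status provides evidence that the participant remained in CR", with minimal OCS maintained.

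Items 6 and 7 neither repeat that condition nor refer to it. Both import the time-to-CDA censoring rules of item 4. A participant who does not reach the state in the treatment phase is censored at its end. One with a main intercurrent event or rescue beforehand is censored at day 267 or later.

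The dates are used again in SAP 3.5.2 for the NCOD and cumulative-dose subperiods: "Details on how to derive the time till CDA, CR, CRmin, CR/PRoff and CRoff are included in section 4.1.4".

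**The concern.** The second route uses only the start of the sequence. What happens to the participant over the next 56 days is not an input. A programmer who follows the text would record an 8-week remission that did not happen. Because the earlier date wins, a later genuine remission would also be dated too early. The curves would then describe time to first touching CR at a low dose, shifted by a constant, rather than time to sustained remission.

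The second route is not a rare one. Under Table 7 of protocol 6.8.1.3, with each step held for its 2-week minimum, a participant of 50 to <75 kg goes from minimal OCS to none in 2 × 2 = 4 weeks, and one of 75 to <100 kg in 3 × 2 = 6 weeks. Such participants do not spend 8 weeks on minimal OCS unless the taper is delayed. If they are in CR from the start of minimal OCS, their status of CR off OCS for at least 8 weeks begins no earlier than week 4 + 8 = 12 or 6 + 8 = 14 after that start. Start + 8 weeks comes sooner and sets the date.

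The censoring for rescue or intercurrent events does not catch these cases. A first relapse is met with an oral prednisone increase (protocol 6.8.1.3), rescue follows a second relapse (protocol 6.8.3), and oral steroid is not on the intercurrent-treatment list (SAP 4.1.2.1).

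**Working it through.** **Day arithmetic.** SAP 2.2.4 sets the target day at 7 × week + 1. Week 36 is 7 × 36 + 1 = 253, and 253 + 14 = 267, which reproduces the SAP's censoring day. Week 28 is day 197. Eight weeks are 56 days. I take the treatment phase to end on day 253.

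**The rule applied to examples (CRmin).** The written rule here includes censoring at the end of the treatment phase.

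| Sequence | Start + 56 | As written | With 56-day persistence |
|---|---|---|---|
| Days 99–113, then relapse | 155 | event, day 155 | censored, day 253 |
| Days 99–147, then relapse | 155 | event, day 155 | censored, day 253 |
| Days 99–155 or longer | 155 | event, day 155 | event, day 155 |
| Starts day 198 | 254 | censored, day 253 | censored, day 253 |
| Starts day 211 | 267 | censored, day 253 | censored, day 253 |
| Starts day 225 | 281 | censored, day 253 | censored, day 253 |

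The rules differ only in the first two rows. The latest start that can give an event is day 253 − 56 = 197, or 255 − 56 = 199 if the week-36 visit falls at the end of its 2-day window.

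**Displaced date.** Suppose a sequence on days 99–113 fails and a second one starts on day 169 (week 24) and holds. The true date is 169 + 56 = 225. The written rule gives 99 + 56 = 155, which is 70 days early.

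**Size, under assumed inputs.** The documents give no rates, so these are assumptions: 70% of an arm reach CR at minimal dose; the start is uniform over weeks 9 to 34; 60% or 80% of sequences last 8 weeks, independently of start; rescue and intercurrent events are not modelled.

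- Start early enough to finish by week 36: (28 − 9)/(34 − 9) = 19/25 = 0.76.
- Events as written: 0.70 × 0.76 = 53.2%.
- Events with true persistence: 53.2% × 0.60 = 31.9%, or 53.2% × 0.80 = 42.6%.
- Excess: 21.3 or 10.6 percentage points.

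**Power, same model** (60 per arm, log-rank, durations exponential, end-of-treatment censoring in both rules; simulated, so approximate).

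| Assumed drug effect | As written | With persistence |
|---|---|---|
| Reach 70% in both arms; persistence 50% vs 85% | 6% | 57% |
| Reach 50% vs 80%; persistence 80% in both arms | 71% | 53% |

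The written rule is nearly blind to an effect on sustaining remission and somewhat more sensitive to an effect on reaching it. The direction depends on the assumed drug effect and is not fixed by the plan.

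**The case against.** The best defence is that the bullets date when CRmin was achieved, and CRmin is a defined term that requires 8 weeks. Read with the definition, the endpoint title and the week-36 rule, the second route merely joins several short episodes, such as minimal OCS followed by off OCS, into one 8-week state. A short remission that relapses is then not CRmin at all. This is probably what was intended, and it makes the defect an omitted condition rather than a decision to count relapsers. But the bullets are the operational derivation, and the SAP found it necessary to write the condition out in 4.1.3.1. The text should not leave it to inference here.

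Three stronger readings are tempting, and the documents do not support them.

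- **Sequences starting after about week 28 also become events.** They do not. The imported rule censors at the end of the treatment phase.
- **Item 7 fails in the same way for any brief episode.** Its sequence must alternate between CR off and PR off, so a lone brief episode does not clearly qualify. A short alternating pair followed by relapse does.
- **The trial could not show relapse prevention.** At most this is true of these two curves. Key secondary endpoint 3, time to CRoff (which has no + 56-day route) and the times to relapse do not use this rule.

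Some disagreement between these curves and CRmin at week 36 is also expected, since first achieved at any time differs from status at a visit.

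**Conclusion.** The point holds as a defect of the written derivation. Items 6 and 7 omit the 56-day persistence condition that the SAP's own definition and week-36 CRmin rule require. If programmed as written, they give false events and dates that are too early. Under the assumed inputs the excess is about 11 to 21 percentage points of participants. Those inputs are illustrative, and censoring for rescue or intercurrent events would remove some of the excess. No general statement about power is supported.

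The reach is limited. The primary endpoint, the key secondary endpoints (including NCOD over the whole on-IMP period) and the alpha-controlled sequence are untouched. Affected are the two time-to-event analyses, which SAP 8.1 lists for the interim and topline outputs, and the NCOD and cumulative-dose subperiods until CRmin and until CR/PRoff. It should be corrected because the remedy is small and already drafted elsewhere in the SAP.

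**What to change.** Add to the second bullet of both items that the sequence must continue for at least 56 consecutive days, with every status in it qualifying and no relapse, using the persistence wording of SAP 4.1.3.1 item 4. If a sequence falls short, search the next one. If none qualifies, censor under the existing rules. Item 7 should also say whether a single episode counts as a sequence. State in SAP 3.5.2 that the subperiods until CRmin and until CR/PRoff use the corrected dates.

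The cost is one sentence per item and a small programming change. Fewer CRmin and CR/PRoff events will be reported. If the programmers already apply persistence, the results do not change.
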